**CGIC:**

- The proportion of patients who are a treatment success, based on the CGIC at each visit that this is measured. A treatment success is defined as Much or Very Much Improved on the CGIC from Baseline of this study.

**PGIC:**

- The proportion of patients who are a treatment success, based on the PGIC at each visit that this is measured. A treatment success is defined as Much or Very Much Improved on the PGIC from Baseline of this study.

**mCDQ-24:**

- The change in mCDQ-24 (Modified Craniocervical Dystonia Questionnaire) from Baseline of this study at each visit that this is measured.

The efficacy measure and endpoint in Part B is as follows:

- Primary efficacy endpoint: change from Pre-Withdrawal Visit total motor AIMS score as assessed by blinded central video rating to the Post-Withdrawal Visit between patients treated with SD-809 and patients treated with placebo.

### **2.3. Sample Size and Power Considerations**

Because this is an open-label study, the sample size is not based on statistical considerations.

It is estimated that approximately 91 patients per arm in the Randomized Withdrawal Period will enable a power of at least 90% to detect a beneficial effect of 1.4 points or more in the change from pre-withdrawal to post-withdrawal in centrally read AIMS when the SD-809 arm is compared to placebo, assuming a standard deviation of 2.9 and a 2-sided type I error rate of 5%.

At the time of finalizing this SAP, all patients have started Part B, or completed part A, or have withdrawn from Part A. 143 patients were randomized to Part B, resulting in a power of approximately 80%.

### **2.4. Randomization and Blinding**

At the beginning of the Randomized Withdrawal Period, patients will be randomized in a blinded fashion to either SD-809 (current dose) or placebo in a 1:1 ratio stratified by DRA status.

## **2.5. Sequence of Planned Analyses**

### **2.5.1. Interim Analyses 1**

The first interim analysis was conducted for the purpose of preparing the integrated summary of safety for the NDA submission. The interim analysis will be based on patient data accrued as of 30-Jun-2016.

### **2.5.2. Interim Analyses 2**

A second interim analysis was conducted for the purpose of preparing an integrated summary of safety. The interim analysis was based on patient data accrued as of 1-Dec-2018.

### **2.5.3. Final Analyses and Reporting – Part A and B**

Final analyses for Part A and B of this study will be performed after the last patient that enrolled into Part B has completed Part B of the study.

### **3. POPULATIONS /ANALYSIS SETS**

#### **3.1. Intent-to-Treat Population**

The Intent-to-Treat (ITT) population will include all patients who were enrolled in the study, regardless of whether or not a patient received a dose of study drug.

#### **3.2. Safety Population**

The Safety population will include all patients who were administered any study drug. Patients who were enrolled but withdrew prior to dosing will not be included in the safety population.

#### **3.3. Randomized Withdrawal ITT Population**

The randomized withdrawal ITT population will include all patients enrolled in Part B of the study.

#### **3.4. Randomized Withdrawal Modified Intent-to Treat Population**

The randomized withdrawal modified intent-to-treat (mITT) population will include all patients enrolled in Part B who receive study drug during the Randomized Withdrawal Period and have a total motor AIMS score as assessed by blinded central video rating at both the Pre-Withdrawal Visit and the Post-Withdrawal Visit.

## **4. GENERAL ISSUES FOR DATA ANALYSIS**

### **4.1. General**

Descriptive statistics for continuous variables include n, mean, standard deviation, standard error, median, minimum, and maximum. Descriptive statistics for categorical variables include patient counts and percentages.

### **4.2. Specification of Baseline Values**

Baseline of this study is the last observed data on or prior to the first dose of drug in the present study (SD-809-C-20). Some of the data used for baseline of this study will come from the parent study (see [Table 1](#)). For baseline data that is coming from the parent study, baseline of this study will be the last observed data collected during the follow-up phase of the parent study. If data are not collected or are missing during the follow-up period in the parent study, then baseline of this study will be the last observed data on or prior to the first dose of drug in the parent study.

### **4.3. Scoring for Rating Scales**

A detailed description for all rating scales below can be found in the protocol.

The AIMS is composed of 12 clinician-administered and scored items. The total motor AIMS score is the sum of items 1 through 7.

The mCDQ-24 is composed of 24 self-administered questions and has 5 domains. The mCDQ-24 questions are rated on a 5-point scale from 0 (never or not at all) to 4 (always or very severely). Patients are instructed to indicate how they felt during the past two weeks because of their abnormal movements by selecting one of the five statements for each question. Following are the domains assessed in the mCDQ-24:

- Stigma (questions 7, 8, 9, 10, 18, 22)
- Emotional wellbeing (questions 11, 12, 13, 14, 15)
- Pain (questions 4, 5, 21)
- ADL (questions 1, 2, 3, 6, 19, 20)
- Social/family life (questions 16, 17, 23, 24)

Each raw domain score is calculated as the sum of the questions in the particular domain. For each domain, raw sub-scores (sum of the individual question scores) will be calculated and then linearly transformed to a 0–100 scale, where a score of 0 indicates the best and a score of 100 the worst possible score. The total score (sum of the raw sub-scores) is similarly transformed to a 0–100 scale (best to worst score).

The UPDRS motor (part III) consists of the 27 questions related to motor functions in part III of the UPDRS scale. Each of the ratings is assessed on a 5-point scale from 0 to 4, with higher values indicating increasing severity/intensity/frequency. The UPDRS motor score is the sum of the 27 questions in part III. The UPDRS subscale scores are balance (items 27, 30), bradykinesia (items 19, 31), movements (items 23A-B, 24A-B, 25A-B, 26A-B), posture and gait (items 28,

29), rigidity (items 22A-E), speech (item 18), and tremor (20A-E, 21A-B). The subscale scores are calculated as the sum of the individual items.

The BARS is composed of 4 items: an objective assessment of akathisia, two subjective measures (self-awareness of restlessness and distress related to restlessness), and a global clinical assessment. The objective assessment of akathisia, and subjective assessments of self-awareness, restlessness and distress related to restlessness are assessed on a 4-point scale from 0-3, with higher values indicating increasing severity/intensity/frequency. A summary score is calculated based on these 3 items resulting in a total score ranging from 0 to 9. The Global Clinical Assessment of Akathisia uses a 6-point scale ranging from 0 (absent) – 5 (severe).

The HADS is composed of 14 items, 7 each for anxiety and depression. The anxiety subscale is the sum of items 1, 3, 5, 7, 9,11, and 13, and the depression subscale is the sum of items 2, 4, 6, 8, 10, 12, and 14.

The ESS is composed of 8 self-administered questions on a 4-point Likert scale (0 to 3). The ESS total score is the sum of 8 questions and can range between 0 and 24 with higher scores indicating a higher level of daytime sleepiness.

The MoCA® is composed of 11 items. The MoCA® total score is the sum of the 11 items. Item 11 is used to correct for patients with 12 years of education (or less) and is only included in the sum when total score is <30. The maximum total possible score is 30 points, indicating no cognitive impairment.

#### **4.4. Handling Withdrawals and Missing Data**

Data summarization for a visit will be based on observed data only.

For AIMS assessed by the site rating, if a response to 1 question is missing, the missing response will be replaced with the average of the remaining responses. If responses to 2 or more questions are missing, the missing responses will not be replaced and the total score will be set to missing.

For mCDQ-24, if a response to 1 question within a domain is missing, the missing response will be replaced with the average of the remaining responses within the domain; if responses to 2 or more questions within a domain are missing, the missing responses will not be replaced and the domain score will be set to missing; if at least 1 domain score is missing then the total score will be set to missing.

For UPDRS motor (part III), if responses to 5 or fewer questions are missing, the missing responses will be replaced with the average of the remaining responses. If responses to 6 or more questions are missing, the missing responses will not be replaced and the total score will be set to missing.

For HADS, if a response to 1 question within a subscale is missing, the missing response will be replaced with the average of the remaining responses within the subscale. If a response to 2 or more questions within a subscale are missing, the missing responses will not be replaced and the subscale score will be set to missing.

For ESS, if responses to 2 or fewer questions are missing, the missing responses will be replaced with the average of the remaining responses. If responses to 3 or more questions are missing, the missing responses will not be replaced and the total score will be set to missing.

For all other rating scales, if any response is missing then the total or subscale score will be set to missing.

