#### **7.1.11. Other Safety Assessments**

Summary statistics for the UPDRS motor score and subscale scores will be presented at baseline of this study and each Part A visit that this is measured. UPDRS motor score and subscale scores values and changes from baseline of this study to each visit will be summarized using descriptive statistics.

Summary statistics for the BARS summary score will be presented at baseline of this study and each Part A visit that this is measured. BARS summary score values and changes from baseline of this study to each visit will be summarized using descriptive statistics.

Summary statistics for the HADS depression and anxiety subscales scores will be presented at baseline of this study and each Part A visit that this is measured. HADS subscale values and changes from baseline of this study to each visit will be summarized using descriptive statistics.

Summary statistics for the C-SSRS baseline version will be presented at screening and for the C-SSRS last visit version will be presented at baseline of this study and each Part A visit that this is measured. Patients with suicidal ideation and behavior items as well as self-injurious behavior without suicidal intent will be summarized at each visit as categorical data using descriptive statistics.

Also for C-SSRS, patients with suicidal ideation and behavior items as well as self-injurious behavior without suicidal intent will be summarized at anytime postbaseline as categorical data using descriptive statistics. Shifts (yes, no) from baseline of this study to anytime postbaseline will be summarized using patient counts for the suicidal ideation and behavior categories as well self-injurious behavior without suicide intent.

Summary statistics for the ESS total score will be presented at baseline of this study and each Part A visit that this is measured. ESS total score values and changes from baseline of this study to each visit will be summarized using descriptive statistics.

Summary statistics for the MoCA® total score will be presented at baseline of this study and each Part A visit that this is measured. MoCA® total score values and changes from baseline of this study to each visit will be summarized using descriptive statistics.

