#### **7.2.7. Other Safety Assessments**

Summary statistics for the UPDRS motor score and subscale scores will be presented at the Pre-Withdrawal Visit and each Part B visit that this is measured. UPDRS motor score and subscale scores values and changes from the Pre-Withdrawal Visit to each visit will be summarized using descriptive statistics.

Summary statistics for the BARS summary score will be presented at the Pre-Withdrawal Visit and each Part B visit that this is measured. BARS summary score values and changes from the Pre-Withdrawal Visit to each visit will be summarized using descriptive statistics.

Summary statistics for the HADS depression and anxiety subscales scores will be presented at the Pre-Withdrawal Visit and each Part B visit that this is measured. HADS subscale values and changes from the Pre-Withdrawal Visit to each visit will be summarized using descriptive statistics.

Summary statistics for the C-SSRS last visit version will be presented at the Pre-Withdrawal Visit and each Part B visit that this is measured. Patients with suicidal ideation and behavior items as well as self-injurious behavior without suicidal intent will be summarized at each visit as categorical data using descriptive statistics.

Summary statistics for the ESS total score will be presented at the Pre-Withdrawal Visit and each Part B visit that this is measured. ESS total score values and changes from the Pre-Withdrawal Visit to each visit will be summarized using descriptive statistics.

Summary statistics for the MoCA® total score will be presented at the Pre-Withdrawal Visit and each Part B visit that this is measured. MoCA® total score values and changes from the Pre-Withdrawal Visit to each visit will be summarized using descriptive statistics.

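### Read literally, the SAP lets any one of five of the seven UPDRS motor subscales be tabulated with none of its own items observed

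*SAP*

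**What the plan says.** SAP 4.3 defines the total: "The UPDRS motor score is the sum of the 27 questions in part III". It assigns the items to seven subscales and adds: "The subscale scores are calculated as the sum of the individual items".

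SAP 4.4 gives the missing-item rule for UPDRS motor: "if responses to 5 or fewer questions are missing, the missing responses will be replaced with the average of the remaining responses". Above that limit: "If responses to 6 or more questions are missing, the missing responses will not be replaced and the total score will be set to missing". Neither sentence mentions the subscales.

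In the same section, HADS and mCDQ-24 allow one missing item per subscale or domain, replace it from items of that same subscale or domain, and set the score to missing at two or more. The closing default, which sets a total or subscale to missing if any item is missing, covers only scales not already given a rule, so it does not reach UPDRS.

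The subscales are reported. For Part A (SAP 7.1.11): "UPDRS motor score and subscale scores values and changes from baseline of this study to each visit will be summarized". For Part B (SAP 7.2.7): "UPDRS motor score and subscale scores values and changes from the Pre-Withdrawal Visit to each visit will be summarized". SAP 7.2.1 presents the Part B safety summaries by randomised arm.

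**The concern.** A subscale exists to show a localised change, such as rigidity or gait worsening while tremor does not. If a whole block is left unrated at a visit and filled from the rest of the motor examination, the table shows a number that contains no information from that block. The value is pulled toward the patient's other items. It can appear as improvement in a patient whose rigidity is unchanged, or as worsening in a patient who has none. Protocol 6.9.9.1 uses the motor items to screen for and monitor parkinsonism, so the subscale tables should reflect what was examined.

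The six-or-more case leaves a second gap. Items are then not replaced and the total is missing, but nothing says whether a partly observed subscale is summed over what is there, which would understate it, or set to missing.

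**Working it through.** **Inputs.** Item lists from SAP 4.3; the limit of 5 and the replacement value from SAP 4.4; item range 0 to 4 from SAP 4.3.

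**Step 1: reproduce the item count.** Balance 2 + bradykinesia 2 + movements 8 + posture and gait 2 + rigidity 5 + speech 1 + tremor 7 = 27. This matches the SAP's figure, and no item sits in two subscales.

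**Step 2: compare each subscale with the limit of 5.**

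| Subscale | Items | Fewest observed with 5 missing overall |
|---|---|---|
| Speech | 1 | 0 |
| Balance | 2 | 0 |
| Bradykinesia | 2 | 0 |
| Posture and gait | 2 | 0 |
| Rigidity | 5 | 0 |
| Tremor | 7 | 7 − 5 = 2 |
| Movements | 8 | 8 − 5 = 3 |

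Five of the seven can be wholly replaced, taken one at a time.

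**Step 3: how many in the same record.** Speech plus two of the two-item subscales uses 1 + 2 + 2 = 5 items, so three are possible. The smallest set of four needs 1 + 2 + 2 + 2 = 7, which exceeds the limit. All five need 1 + 2 + 2 + 2 + 5 = 12. The maximum is three. Rigidity can be wholly replaced only when its five items are the only ones missing.

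**Step 4: value produced.** If all five rigidity items are missing and the other 22 sum to S, the rule gives rigidity = 5 × S/22, on a scale of 0 to 20. The records below are constructed for illustration.

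- True rigidity 10, unchanged, S = 6: 5 × 6/22 = 1.36. The apparent change is 1.36 − 10 = −8.64. The total becomes 6 + 1.36 = 7.36 instead of 16.
- True rigidity 10, unchanged, S = 11: 5 × 11/22 = 2.5, an apparent change of −7.5.
- True rigidity 0, unchanged, S = 11: 2.5, an apparent change of +2.5.

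**Step 5: what one such record does to a group mean.** SAP 2.3 reports 143 patients randomised 1:1, so about 143/2 = 71.5 per arm. One record with an error of −8.64 moves an arm mean by 8.64/71.5 = 0.12. Against the roughly 330 patients planned for Part A, it moves the mean by 8.64/330 = 0.03. Both assume that every patient contributes at that visit.

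**The case against.** The strongest counter-argument is that the UPDRS rule names only the total as its result, whereas the HADS and mCDQ-24 rules name the subscale or domain. It could have been meant for the total alone. The SAP indeed does not say outright that replaced items feed the subscales; that is the literal reading of 4.3 with 4.4. But if the rule is for the total only, the SAP has no missing-item rule for the UPDRS subscales at all. Either reading calls for added text. The opening sentence of 4.4, which bases visit summaries on observed data, does not settle it, because item-level replacement rules follow directly.

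A reader might infer that UPDRS is the only scale in 4.4 with scale-wide replacement. It is not: the site-rated AIMS and ESS rules are also scale-wide. UPDRS stands apart only among the scales with reported subscales or domains.

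A reader might also infer that parkinsonism would go undetected. The documents do not support that. Parkinson-like adverse events are summarised with Kaplan-Meier curves and exposure-adjusted rates (SAP 7.1.3), and neurological examinations are listed (SAP 7.1.9). The listed endpoint is UPDRS Part III itself; the subscales appear only in descriptive summaries.

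Finally, the large individual errors come from constructed records, and a single one barely moves a group mean. That stands.

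**Conclusion.** The point holds in limited form. Followed literally, the SAP gives a value to a subscale in which nothing was measured, for any one of five of the seven subscales and at most three in one record. It should not be read as all five being affected together, which would need 12 missing items. With 6 or more items missing, the subscale handling is unstated.

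The error in an individual record can be large (−8.64 on a 0 to 20 subscale in the constructed case). The effect on the tables depends on how often whole blocks go unrated, which the documents do not report; it may be small. Only descriptive safety summaries are touched. The primary Part B analysis uses centrally rated AIMS and is unaffected. The conclusion rests on the literal combination of SAP 4.3 and 4.4 and on the item counts, not on any assumed distribution of scores.

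**What to change.** Amend SAP 4.4 for UPDRS as follows.

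- State that the existing five-item rule applies to the 27-item total only.
- For subscales, replace a missing item only with the mean of the observed items in the same subscale, and only when a stated minimum is observed. At least half is one option: 1 of 2 for balance, bradykinesia, and posture and gait; 3 of 5 for rigidity; 4 of 7 for tremor; 4 of 8 for movements. Speech has one item, so it is either observed or missing.
- Otherwise set that subscale to missing.
- State that this subscale rule applies whatever the number of items missing overall, which closes the six-or-more gap.

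The half threshold is a choice, not a figure from the documents. In a two-item subscale it copies the single observed item. A limit of one missing item, as for HADS and mCDQ-24, would also serve, provided at least one item is observed.

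The total should not be set to missing whenever a whole subscale is unobserved. Speech is a single item, so one missing rating would then void a 27-item total, while five missing tremor items would not. Keeping the total rule means accepting that the total can carry the distortion shown in Step 4.

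The cost is a few lines of SAP text and programming. A few visits lose a subscale value that was not measured.

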#### 4.5. Study Days and Visit Windows

Study days will be numbered relative to the 1st day of study drug administration. The start of treatment (day 1) is defined as the date on which a patient takes the 1st dose of study drug. Days will be numbered relative to study start (ie, ..., -2, -1, 1, 2, ...; with day 1 being the start of study drug and day -1 being the day before the start of study drug).

##### **Part A Visits:**

For efficacy and safety by-visit analyses, data collected at post baseline scheduled visits will be included using their scheduled visit and data collected at early termination and unscheduled visits will be included and assigned to a visit window as described below. After the assignments are made use the following rules: if there is a scheduled visit with an early termination and/or unscheduled visit in the same visit window, the scheduled visit will be used in the analysis; if there is no scheduled visit but an early termination and unscheduled visit in the same visit window, the early termination visit will be used in the analysis; if there is no scheduled or early termination visit but an unscheduled visit in a visit window, the unscheduled visit will be used in the analysis.

Efficacy: Visit Windows for Early Termination and Unscheduled Visits

Visit	Study Day		
	AIMS site	CGIC, PGIC	mCDQ-24
Week 2	2 to 21		
Week 4	22 to 35	2 to 35	
Week 6	36 to 74	36 to 74	2 to 74
Week 15	75 to 151	75 to 151	75 to 151
Week 28	152 to 242	152 to 242	152 to 242
Week 41	243 to 328	243 to 328	243 to 328
Week 54	329 to 424	329 to 424	329 to 560
Week 67	425 to 515	425 to 515	
Week 80	516 to 606	516 to 606	
Week 93	607 to 697	607 to 697	
Week 106	698 to 788	698 to 788	561 to 924
Week 119	789 to 879	789 to 879	
Week 132	880 to 970	880 to 970	
Week 145	971 to 1061	971 to 1061	
Week 158	1062 to 1110	≥1062	≥925
Follow-up	≥1111		

## Safety: Visit Windows for Early Termination and Unscheduled Visits

Visit	Study Day						
	[1]	[2]	[3]	[4]	[5]	[6]	[7]
Week 2	2 to 21	2 to 21				2 to 21	2 to 21
Week 4	22 to 35	22 to 35				22 to 67	22 to 35
Week 6	36 to 74	36 to 119	2 to 119	2 to 74	2 to 210		36 to 74
Week 15	75 to 151			75 to 151		68 to 151	75 to 151
Week 28	152 to 242	120 to 242	120 to 287	152 to 242		152 to 242	152 to 242
Week 41	243 to 328	243 to 328		243 to 328		243 to 378	243 to 328
Week 54	329 to 424	329 to 560	288 to 560	329 to 424	211 to 560		329 to 424
Week 67	425 to 515			425 to 515		379 to 515	425 to 515
Week 80	516 to 606			516 to 606		516 to 606	516 to 606
Week 93	607 to 697			607 to 697		607 to 742	607 to 697
Week 106	698 to 788	561 to 924	561 to 924	698 to 833	561 to 924		698 to 833
Week 119	789 to 879					743 to 879	
Week 132	880 to 970			834 to 1015		880 to 970	834 to 1015
Week 145	971 to 1061					971 to 1110	
Week 158	1062 to 1110	≥925	≥925	≥1016	≥925		≥1016
Follow-up	≥1111					≥1111	

[1] Vital signs, weight, UPDRS, BARS, HADS, C-SSRS; [2] ECG; [3] Laboratory tests; [4] MoCA®; [5] Standing, Supine, and Orthostatic heart rate and blood pressure; [6] Sitting heart rate and blood pressure; [7] ESS.

